The aim of this study is to assess the effects of clinician racial bias on end-of-life communication and to develop interventions to reduce the effects of implicit bias on quality of clinician communication. There are two study objectives: (1) Establish which communication behaviors in the end-of-life setting are most affected by clinician implicit racial bias and explicit stereotyping. (2) Pilot a theory-driven intervention to improve clinician communication and reduce disparities in quality end-of-life care. These objectives will be met in two study phases.

Methods/Design:**Phase 1:****Methods:**

(1) I will develop a case depicting a hospitalized 72-year-old with lung cancer and sepsis due to pneumonia on high-flow nasal cannula with my mentorship team of experts in palliative medicine and critical care. I will design a clinical encounter with the caregiver to discuss goals of

Protocol #

care. 2) The caregiver encounter will be piloted with critical care and hospitalist physicians at Montefiore to ensure realism and achieve standardization.¹⁰⁸ Black standardized caregivers will be recruited from the pool of actors used by the Einstein Clinical Skills Center. (3) Standardized caregivers will be trained in the use of a communication assessment tool.¹⁰⁹ (4) 50 physicians will be recruited to participate in a videotaped high-fidelity simulation of the encounter. The session will be followed by a 1-hour communication skills training to allow participants to earn continuing medical education (CME) credit. (5) Immediately after the simulation subjects will complete the IAT and a questionnaire probing for attitudes about race and end-of-life care along with demographic questions. We will assess training needs by adapting a previously developed questionnaire measuring physicians' self-identified serious illness communication training needs by incorporating questions about bias mitigation skills.¹¹⁰ The IAT is publicly available here: <https://implicit.harvard.edu/implicit/selectatest.html>.

COVID-19 Concerns:

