of group assignment. Block randomization will occur with randomly mixed block sizes of 2, 4, and 6. The allocator (research assistant) will hide block size from the executor (PI) in order to prevent the executor from predicting the next assignment. Randomization will be carried out by having a piece of paper that has the phrase “Intervention (Communication + Bias)” or “Control (Communication only)” placed inside an opaque envelope. The outside of the envelopes will be labeled with the sequence number. After a subject has been enrolled into the study and consented, the next sequence numbered envelope on the stack will be opened to determine the study group that the subject will enter.

Participants will be videotaped during high-fidelity simulations of encounters with caregivers described in phase 1, before and after receiving the intervention or control. The intervention and simulations will take place in one half-day workshop.

COVID-19 Concerns:

The Clinical Skills Center will be holding in-person simulations with standardized patients for the purposes of medical education starting in May 2021. The simulations in this study will not begin until after that time and will involve less risk than typical simulations because they will not entail a physical examination of the standardized caregiver. Actors and participants will be equipped with personal protective equipment including surgical masks. Trainers and participants in the training session will be required to wear provided surgical masks and remain six feet apart during the training sessions. If COVID-19 state or institutional guidelines prohibit these types of encounters at the time the simulations will be launched, the simulations and training will be adapted to a virtual format and nonverbal behavior coding will be adjusted. These changes will be submitted to the IRB as an amendment.

Study population and Recruitment:

Protocol #

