A new group of intensivists, oncologists, emergency medicine physicians and hospitalists will be recruited including resident and fellow trainees in those specialties. Physician subjects will be recruited face-to-face by the PI, through departmental email blasts and emails to contacts of the study team. As in phase 1, physicians will complete a screening questionnaire to exclude those that do not routinely encounter hospitalized patients with a life expectancy of less than one year. Potential subjects will be asked about the frequency and timing of previous communication and bias training. Physicians practicing Hospice and Palliative Medicine will be excluded because of their extensive prior training in communication.

Data collection:

Encounters will be videotaped. We will use the five-point verbal communication rating scale and nonverbal communication behaviors coded with the NAAS during the standardized encounter as described in phase 1 above.^{111,114} A research assistant who did not participate in the training sessions and is blinded to participant group will code communication behaviors. Subjects will complete the IAT and the questionnaire described in phase 1 immediately after the first encounter.

Outcome measures:

Subjects will complete an on-line questionnaire at the close of the session with Likert-type questions on the usefulness and acceptability of the training program and self-efficacy with cross-cultural communication. In addition, the questionnaire will include the cognitive and affective empathy portions of the Interpersonal Reactivity Index. For participants in the active group only, several questions will assess the illusion of ownership of the virtual body in the VR experience. An open-ended text box will invite feedback. The primary efficacy endpoint will be verbal dominance (ratio of clinician to patient speaking time during the encounter with a ratio of >1 meaning that the clinician dominated the discussion).⁹⁹ Secondary endpoints will include

Protocol #

verbal and nonverbal communication and encounter duration. Inter-rater reliability for the communication scores will be reported using Kappa values.

Analysis plan:

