Potential risks: This research poses two main risks to subjects: 1) emotional distress and 2) risk to privacy. There may be some emotional distress caused by learning about one's unconscious racial biases. Emotional distress may also result from passive deception; subjects will not be told that racial bias is the focus of the study until after the intervention. Privacy risk arises because racial biases may be considered sensitive information about the subject.

Adequacy of Protection Against Risks

Recruitment and Informed Consent: All subjects will be recruited by the PI through departmental email blasts, emails to contacts of the study team and departmental faculty meeting presentations. The consent process will take place in the Clinical Skills Center on the prior to the standardized patient encounter. Subjects will be informed of their right to participate or discontinue participation at any time without jeopardizing their employment, professional position or relationships with colleagues. Copies of the signed consent form will be given to the subject and placed in the subject's research folder in a locked file drawer in an office in the PI's office expressly designed for this purpose.

Incomplete disclosure of information during the consenting process: Subjects will be informed that they are participating in a study exploring physician cognition, cognitive biases and communication behavior. They will be informed that study participation includes completion

Protocol #

of an on-line instrument after the standardized patient encounter. They will not be told during the consent process that implicit racial bias and stereotyping are the focus of the study.

Incentives: Incentives have been chosen to provide a counterbalance to the opportunity costs of participating by offering continuing medical education (CME) credits for attending physician participants. Given that CME credits can be obtained in many ways, this incentive is not to be enough to be coercive. Since resident and fellow participants are unable to use CME credits during training, they will be offered a \$50 gift card to compensate them for their time.

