Protections against risks: Personal identifiers not be collected in the on-line instrument; instead a unique study ID will be assigned to each participant. Video recordings will be maintained in a password protected digital folder on a hard drive in a locked office. This database of coded communication scores will be stripped of participant identifiers as soon as all data is collected, and a file linking the study ID and patient identifiers will be kept in a separate, password protected digital folder.

Debriefing: After completion of the on-line bias measurement instrument, the subjects will be shown a debriefing statement including full disclosure of the aims of the study and the intent to examine the relationship between implicit racial bias and stereotyping and communication behavior. This statement will include a reminder that they may discontinue participation at any time and request that their data be removed from the dataset without penalty. The PIs contact information will be provided.

Potential Benefits of the Proposed Research: Subjects are not expected to directly benefit from this research.

[figure not shown]
Importance of the knowledge to be gained: The information from this study will provide knowledge about the role of implicit bias and stereotyping in communication behaviors that have

Protocol #

profound effects on the quality of end of life care for black patients. It will also inform efforts to mitigate the effects of this bias in future studies.

Necessity of withholding information in the consent process: Withholding of complete information from the consent process is only acceptable if there is no reasonably effective alternative to achieve the goals of the research. In this case, knowledge of the intent to study implicit racial bias is likely to affect the way physicians communicate in the standardized patient encounter, thus invalidating the results of the study.

Figures:

References:

1. Chartbook on Health Care for Blacks. Part 1: Overviews of the Report and the Black Population. Agency for Healthcare Research and Quality, 2015. (Accessed June 21, 2019, 2019, at <https://www.ahrq.gov/research/findings/nhqrdr/chartbooks/blackhealth/part1.html>.)

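### Participants who have been told the racial-bias aim could pass it, and the reused case, to colleagues recruited later, and the protocol describes no safeguard

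*Combined protocol and SAP*

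**What the plan says.** All places are in the combined protocol and SAP.

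- **Why the aim is withheld.** The paragraph on the necessity of withholding information argues that a physician who knows implicit racial bias is being studied will probably communicate differently in the encounter, "thus invalidating the results of the study".
- **When it is disclosed.** Under Debriefing, once the on-line bias instrument is done, "the subjects will be shown a debriefing statement including full disclosure of the aims of the study". In Phase 1 (Methods), "Immediately after the simulation subjects will complete the IAT". In Phase 2 (Data collection), "Subjects will complete the IAT and the questionnaire described in phase 1 immediately after the first encounter".
- **Who comes next.** Phase 2 takes new individuals from the same four specialties, trainees included. Both phases carry the same recruitment sentence: "Physician subjects will be recruited face-to-face by the PI, through departmental email blasts and emails to contacts of the study team". The paragraph on recruitment and informed consent adds departmental faculty meetings.
- **What they meet.** Phase 2, Design: "Participants will be videotaped during high-fidelity simulations of encounters with caregivers described in phase 1". Randomization is by numbered envelope, opened as each subject is enrolled.
- **What safeguards are described.** The debriefing statement is said to cover the aims, the right to stop or withdraw data, and contact details. Screening covers patient exposure and previous communication and bias training. Neither analysis plan mentions prior knowledge of the study.

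**The concern.** The case for incomplete disclosure rests on participants not knowing the focus when they enter the encounter. That has to hold for the last participant as well as the first. By the time Phase 2 opens, up to 50 Phase 1 physicians will know both the case and the aim, and they work in the specialties from which the next 50 are sought. Requiring new individuals in Phase 2 excludes repeat participants but not their informed colleagues.

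If informed physicians guard their behaviour, their verbal dominance no longer reflects their IAT score in the usual way, and the Phase 1 association is weakened or distorted. In Phase 2, informed participants may start from better pre-training scores, leaving less room for a difference between arms. Because no item on prior knowledge is described, affected encounters could not be identified afterwards.

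**Working it through.** **1. Reproduce the plan's power figures.**

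Phase 1 inputs (Power analysis): n = 50, ρ = 0.38, two-sided α = 0.05. With Fisher's z, power ≈ Φ(atanh(ρ)·√(n−3) − 1.96):

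- atanh(0.38) = 0.400 and √47 = 6.856, product 2.743
- Φ(2.743 − 1.96) = Φ(0.783) = 78.3%

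A simulated t-test of the correlation gives 79.1%. Both sit just under the stated figure of more than 80%, near enough to serve as a baseline.

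Phase 2 inputs (Analysis plan): 25 per arm, d = 0.8, two-sided α = 0.05. The noncentral t has 48 degrees of freedom and noncentrality 0.8·√(25/2) = 2.828, giving 79.1%. The normal approximation gives 80.7%. The stated 80% is reproduced.

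**2. Illustrate the effect of leakage.** The documents give no leak rate, so two quantities are assumed: the fraction f of participants who are informed, and the share a of the effect lost in each of them (a = 1 full attenuation, a = 0.5 half). With variances unchanged, the effect shrinks by the factor (1 − a·f).

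Phase 1, ρ = 0.38·(1 − a·f):

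| f | ρ, half | Power, half | ρ, full | Power, full |
|---|---|---|---|---|
| 0 | 0.380 | 78% | 0.380 | 78% |
| 10% | 0.361 | 74% | 0.342 | 69% |
| 20% | 0.342 | 69% | 0.304 | 58% |
| 30% | 0.323 | 63% | 0.266 | 46% |

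For example, with f = 30% and half attenuation, atanh(0.323) = 0.335, times 6.856 = 2.297, and Φ(0.337) = 63%.

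Phase 2, d = 0.8·(1 − a·f), on the same assumption that informed participants lose some or all of the between-arm difference:

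| f | d, half | Power, half | d, full | Power, full |
|---|---|---|---|---|
| 0 | 0.80 | 79% | 0.80 | 79% |
| 10% | 0.76 | 75% | 0.72 | 70% |
| 30% | 0.68 | 65% | 0.56 | 49% |

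The Phase 2 figures are the less secure of the two, for the reasons given under the objection.

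**3. Direction of the effect in Phase 2.** What a participant has heard before arriving precedes randomization, so it is balanced between arms in expectation. The model also adjusts for the pre-intervention score. The expected result is a shifted baseline and possibly a diluted contrast, not a bias favouring one arm.

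**The case against.** **Leakage is a possibility, not an established fact.** A reader might infer that concealment will fail. The documents do not support that. They give no leak rate and no recruitment calendar, do not say that Phase 2 draws on the same departments, and allow contacts of the study team who may work elsewhere. Phase 2 runs as a workshop ("The intervention and simulations will take place in one half-day workshop") with small-group debriefing, so participants may be seen in batches, which would limit the opportunity. This stands.

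**The absence of a safeguard is only partly verifiable.** The debriefing statement and questionnaires are summarised, not reproduced, and consent pages are not available here. A confidentiality request may exist. What can be said is that none is described. This stands too, and if one exists the protocol should say so.

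**The protocol's warning concerns the aim, not the case.** It says nothing about the effect of knowing the scenario. Consent already mentions cognitive biases and communication, so the added effect of hearsay is unknown.

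**Leakage does not hand controls the active ingredient.** A reader might infer that informed controls acquire what the active arm is meant to add. Both Phase 2 arms take the IAT and the racial-attitude questionnaire before training and the second encounter, so controls meet the topic by design. The active arm adds virtual reality (VR), perspective taking, mitigation techniques and role-play. The background section itself doubts that awareness alone has lasting effect. That argument is weak and is not relied on here. One related passage needs reconciling: the Potential risks paragraph states that "subjects will not be told that racial bias is the focus of the study until after the intervention", whereas Debriefing places disclosure after the bias instrument, which in Phase 2 comes before the intervention.

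**Full attenuation is extreme.** The protocol describes implicit bias as unconscious and automatic, so informed physicians are unlikely to lose all association with the IAT. This is why half attenuation is shown alongside.

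What survives is an unaddressed and credible route by which a premise the protocol calls essential could fail undetected.

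**Conclusion.** The point holds as a risk without a described safeguard. Three things combine: full disclosure to participants, the same specialties and recruitment routes in both phases, and reuse of the encounter. Later participants could hear the aim and the case, and the plan as written could not show whether they had.

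The main exposure is the Phase 1 primary association, where 10% to 30% informed would take power from about 78% to 74%–63% with half attenuation, or 69%–46% as the worst case. Both the fraction informed and the degree of attenuation are assumptions. In Phase 2 the expected harm is shifted baselines with some possible dilution. A reader might infer systematic between-arm bias there, but knowledge gained before randomization does not produce it. Phase 2 is a pilot whose stated primary goal is feasibility and preliminary data, which limits the damage but makes it useful to learn whether concealment held. A change is worth making because it is cheap and the information cannot be recovered reliably later.

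**What to change.** 1. **Debriefing statement.** Add a request not to discuss the aims, the case or the VR content with colleagues until Phase 2 enrolment closes. Delaying the statement alone would not be enough, because the IAT, the attitude questionnaire and the Phase 2 training also reveal the focus.
2. **One item in both phases.** Ask, in neutral open-ended wording, what the participant had heard about the study or the case before arriving. Place it right after the first encounter and before the IAT, the debriefing and, in Phase 2, the arm-specific training. Asked at the close of Phase 2, recall could differ by arm, and excluding participants on that answer could bias the randomized comparison.
3. **Sensitivity analysis.** Repeat the primary analysis excluding, or adjusting for, informed participants. In Phase 2, treat awareness as a pre-training covariate or subgroup.

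The cost is one sentence, one questionnaire item and one additional analysis; sample size, randomization and participants' right to full disclosure are unchanged. The downsides are that self-reported awareness is imperfect and that exclusion reduces numbers. In Phase 1, excluding 10% or 30% leaves 45 or 35 participants and, at ρ = 0.38, power of about 74% (0.400·√42 = 2.593) or 62% (0.400·√32 = 2.263). The sensitivity analysis should therefore be read for consistency of the estimate, not as a second test.
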